**Table 5: Time to first event of unscheduled medical attendance, wheeze or cold**

---

ITT population	Montelukast N=	Placebo N=	HR (95% CI)	p-value
----------------	-------------------	---------------	-------------	---------

---

**Time (in days) to first:**  
**Hospital admission**  
**Hospital attendance (A&E or admission)**  
**Unscheduled GP visit**  
**Episode of wheeze**  
**Episode of a cold**

---

Data are median (IQR)

Data are analysed using a Cox regression model with fixed effects for stratification factor and treatment group

**Table 6: Medication usage**

ITT population	Montelukast N=	Placebo N=	IRR or OR (95% CI)	p-value
Steroids (OCS)				
 Number of courses, mean (SD)				
 Proportion receiving OCS, N (%)				
Steroids (ICS)				
 Proportion starting, N (%)				
Salbutamol				
 Number of puffs used per episode, mean(SD)				
Total puffs used per year				
Investigational Medicinal Product				
 Number of initiations, mean (SD)				
 Number of sachets per episode, mean (SD)				
Number of sachets used per year				

Data are analysed using Poisson regression with fixed effects for stratification factor and treatment group and a random effect for individual to account for overdispersion with follow up time fitted as the exposure.

Data are analysed using logistic regression with fixed effects for stratification factor and treatment group

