#### **Secondary objectives**

2.To determine whether the effect of treatment on the primary analysis is different depending upon ALOX5 status (5/5 vs. 5/x and x/x).

3.To determine whether intermittent treatment with oral montelukast in preschool children reduces the time to first medical attendance.

4.To determine whether intermittent treatment with oral montelukast in preschool children reduces the need for each type of medical attention for wheeze: hospital admissions; hospital attendance; and GP visits.

5.To determine whether intermittent treatment with oral montelukast in preschool children reduces the time to first occurrence of each type of medical attention for wheeze: hospital admissions; hospital attendance; and GP visits.

6.To determine whether intermittent treatment with oral montelukast in preschool children reduces the duration of hospital admissions.

7.To determine whether intermittent treatment with oral montelukast in preschool children reduces the number of episodes, duration and time to first event of wheeze and cold.

8.To determine whether intermittent treatment with oral montelukast in preschool children reduces the need for alternative medications (Steroids, Salbutamol).

9.To describe the safety profile of montelukast.

10.To describe parents opinion of treatment efficacy

11.To describe compliance to medication

12.To determine whether baseline urinary eicosanoid level is different across baseline groups: ALOX5 status (A or B), leukotriene genes and, type of wheeze (episodic, multitrigger). **NOTE ANALYSIS DETAIL NOT CONTAINED IN THIS PLAN**

13.To determine whether montelukast is cost effective. **NOTE ANALYSIS DETAIL NOT CONTAINED IN THIS PLAN**

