**Medication use**

Steroids (OCS):

- The number of courses per year (and total number of days) as recorded on the diary card. Each mention of use on a separate diary card indicates a course.
- The proportion receiving none vs. any during the trial as recorded on the diary card or in the phonecall data.

Steroids (ICS):

- Proportion starting ICS during the trial as recorded on the diary card or phonecall data (baseline data (T2) indicates whether child was on ICS at the start of the trial)

Salbutamol:

- Total number of puffs overall per episode of wheeze as recorded on the diary card
- Total number of puffs (Salbutamol use per year)

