## **ANALYSIS OF SECONDARY OUTCOMES**

### **Definition of outcome measure**

individual type of medical attendance: (hospital admission, hospital attendance (a&e), and GP visit)

Duration (in days) of hospital admission

Number of wheeze episodes

Total duration of wheeze episode

The number of steroid (OCS) courses per year

The number of IMP courses per year

first hospital admission

first hospital attendance (A&E)

first GP visit

first episode of wheeze

proportion receiving no steroids (OCS) vs. any during the trial

Proportion starting steroids (ICS) during the trial

Salbutamol use per year

Salbutamol use per episode of wheeze per year

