### **Secondary analysis**

The primary analysis will be repeated for each of the following secondary outcomes:

individual type of medical attendance: (hospital admission, hospital attendance (a&e), and GP visit)

Duration (in days) of hospital admission

Number of wheeze episodes

Duration of wheeze episode

The number of steroid (OCS) courses per year

The number of IMP courses per year

Time to event data will be summarised using Kaplan Meier plots. The treatment effect will be evaluated using a Cox regression model. The Hazard Ratio (HR) for the treatment effect and corresponding 95% confidence interval will be presented. A

HR of less than 1 indicates a benefit of Montelukast in reducing the time to first event.

first hospital admission

first hospital attendance (A&E)

first GP visit

first episode of wheeze

Binary outcomes will be analysed with logistic regression

proportion receiving no steroids (OCS) vs. any during the trial

Proportion starting steroids (ICS) during the trial

Assumption checks and actions to be taken is assumptions do not hold

The assumption of proportional hazards for the cox regression model will be checked using the methods proposed by Grambsch and Therneau. If this assumption is violated, alternative methods will be used.

See section 8.4 for Poisson regression assumption checks.

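### Yearly total salbutamol puffs has no specified model, so the only specified salbutamol comparison is puffs per wheeze episode, which can miss a benefit that comes from fewer episodes

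*SAP*

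**What the plan says.** Objective 8 in the SAP's 'Secondary objectives' is to find out whether treatment "reduces the need for alternative medications (Steroids, Salbutamol". Two salbutamol outcomes serve it under 'Medication use': "Total number of puffs overall per episode of wheeze as recorded on the diary card" and "Total number of puffs (Salbutamol use per year". Both reappear in the 'Definition of outcome measure' list for the secondary outcomes, as "Salbutamol use per year" and "Salbutamol use per episode of wheeze per year".

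The methods text in 'Secondary analysis' opens its Poisson list with "The primary analysis will be repeated for each of the following secondary outcomes". That list covers attendance types, admission duration, number and duration of wheeze episodes, oral steroid courses and IMP courses. Cox and logistic lists follow. Neither salbutamol measure is on any of the three.

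Table 6 has columns for a rate or odds ratio with confidence interval and for a p-value. The row "Number of puffs used per episode, mean(SD" carries footnote 1: Poisson regression with a random effect for individual and follow-up time as exposure. The row "Total puffs used per year" carries no footnote and no summary statistic.

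**The concern.** Taken as written, the plan specifies a formal comparison for one salbutamol measure only, and that measure is not the one that answers objective 8.

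- **Conditioning.** A child with no wheeze episode has no puffs per episode. Montelukast is meant to reduce the number of episodes (objective 7), so the comparison is made in a subset formed after randomisation by something the drug may change. Table 6 is headed as the ITT population, and 'Method for handling non-adherence' promises intention-to-treat for all secondary outcomes. A measure that is undefined for some randomised children cannot deliver that.
- **Exposure.** Follow-up time is a natural exposure for a total. It is not one for an amount already expressed per episode.
- **Status of the result.** 'Multiple comparisons and multiplicity' says that comparisons are defined in advance in this document, and the 'Introduction' requires unplanned analyses to be labelled as such. A model of total puffs added later would be reported as unplanned, while the conditional measure would have pre-specified status.

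**Working it through.** **1. Where each measure has a model**

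| | Puffs per episode | Total puffs per year |
|---|---|---|
| Defined under 'Medication use' | yes | yes |
| Listed as a secondary outcome | yes | yes |
| Model in 'Secondary analysis' | none | none |
| Model in Table 6 | footnote 1 (Poisson) | none |

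The per-episode model therefore rests on a table footnote alone, and the total has no model anywhere.

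**2. How the two measures relate**

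The SAP gives no figure for puffs, so these inputs are assumed. Placebo: 2 mild episodes at 10 puffs and 2 severe episodes at 40 puffs per child-year. The 33% reduction is borrowed from 'Sample size determination', where 0.76 × (1 − 0.33) = 0.509, the stated 0.51.

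Placebo total: 2 × 10 + 2 × 40 = 100 puffs over 4 episodes, or 25.0 per episode. On treatment there are 4 × 0.67 = 2.68 episodes, so 1.32 are prevented.

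| Episodes prevented | Treatment puffs | Total ratio | Puffs per episode | Per-episode ratio |
|---|---|---|---|---|
| Evenly | 1.34 × 10 + 1.34 × 40 = 67.0 | 0.67 | 67.0/2.68 = 25.0 | 1.00 |
| Mild only | 0.68 × 10 + 2 × 40 = 86.8 | 0.87 | 86.8/2.68 = 32.4 | 1.30 |
| Severe only | 2 × 10 + 0.68 × 40 = 47.2 | 0.47 | 47.2/2.68 = 17.6 | 0.70 |

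In each row the per-episode ratio is the total ratio divided by the episode ratio of 0.67. Any benefit that comes through fewer episodes is divided out. The assumed 4 episodes a year cancels; only the mix of mild and severe matters.

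The mild-only case varies with the assumed puffs in a severe episode:
- 20 puffs: total 46.8/60 = 0.78; per episode 17.46/15 = 1.16.
- 80 puffs: total 166.8/180 = 0.93; per episode 62.24/45 = 1.38.

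These are pooled ratios of puffs to episodes. They show the direction of the problem and are not a prediction of what the footnote model would return.

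**3. Effect of the exposure term**

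Take two children who each use 25 puffs in one episode, one followed for 12 months and one for 6. With follow-up time as exposure they contribute 25/1 = 25 and 25/0.5 = 50 per year, although use within the episode is identical.

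**4. How many children could drop out of the per-episode comparison**

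Suppose wheeze episodes followed the SAP's planning figures (mean 0.76, SD 1.22, falling to 0.51) under a negative binomial with common dispersion.
- k = (1.22² − 0.76)/0.76² = 0.7284/0.5776 = 1.261
- P(no episode) = (1 + kμ)^(−1/k)
- Placebo: 1.958^(−0.793) = 0.59. Montelukast: 1.643^(−0.793) = 0.67.

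The planning figures come from oral steroid courses used as a proxy. Diary wheeze may be more frequent and these shares lower. If the drug prevents episodes, the selection would still differ between arms.

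**The case against.** Three points on the other side have force.

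*The total is not hidden.* A reader might infer that a fall in rescue use would go unseen. The SAP does not support that. Total puffs is a row in Table 6 reported by arm, 'Descriptive statistics for outcome measure' promises a summary of each secondary outcome, and the number of wheeze episodes has its own Poisson model. Only the inferential result for the total is missing.

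*The missing footnote may be a slip.* The row for sachets per year also lacks a footnote, and neither row has the mean (SD) label that the marked count rows carry. The table does have ratio and p-value columns. An unfinished table shell is as likely as a decision to leave the total untested, so no intent should be read into it. The gap remains either way, because 'Secondary analysis' does not supply the model.

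*Apparent harm is one case of several.* A reader might infer that the per-episode measure would make an effective drug look harmful. That needs the prevented episodes to be mainly mild, and nothing in the SAP says they would be. If mainly severe ones are prevented, both ratios fall.

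Puffs per episode is also a listed outcome in its own right and describes use within an attack. That is a reason to keep it, properly labelled, and not to drop it.

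**Conclusion.** The point holds as a gap in the specified analysis of one secondary objective. The measure closest to objective 8 has no pre-specified model. The one salbutamol comparison that is specified depends on having a post-randomisation episode and uses an unsuitable exposure. On the assumed puff counts, a 33% fall in episodes gives total and per-episode ratios of 0.67 and 1.00, 0.87 and 1.30, or 0.47 and 0.70, depending on which episodes are prevented. The per-episode result can therefore miss the benefit, move against it or agree with it. That the two measures differ whenever the number of episodes changes does not depend on the assumed counts; the sizes do. The primary outcome and the sample size are unaffected.

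**What to change.** Align the secondary 'Definition of outcome measure' list, 'Secondary analysis' and Table 6 as follows.

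- **Main salbutamol comparison:** total puffs per child, using the overdispersed count model with genotype as covariate and log diary observation time as offset. Observation runs from randomisation to the earlier of 12 months or withdrawal from medication. 'Derived and computed variables' gives this cut-off only for children without cold or wheeze episodes, so its use for diary counts needs to be written down.
- **Zeros and missing counts:** count zero only for a child under diary observation with no salbutamol recorded in either the diary or the phone-call data. Scoring every child without a record as zero would be wrong. The SAP says that diary cards are not completed by those not taking IMP, and under 'Medication use Salbutamol' the phone calls capture other medications used while the puff items are on the diary card. Treat absent diaries, and phone-reported use without diary puffs, as missing puff counts.
- **Puffs per episode:** keep as supportive, labelled as conditional on having an episode, without follow-up time as its exposure.

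The cost is SAP and table-shell wording plus one more model on data already collected. Total puffs is likely to be skewed, so the interval may be wide.

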**Table 7 Total adverse events per group**

Safety population	Montelukast N=	Placebo N=
All events		
	Minor injury	
	GI	
	URTI	
	CNS	
	Minor infection	
	Allergy	
	Cutaneous	
	Respiratory	
	Haem	
Possibly, probably or definitely related		
	Minor injury	
	GI	
	URTI	
	CNS	
	Minor infection	
	Allergy	
	Cutaneous	
	Respiratory	
	Haem	
Data are n (%)		

**Table 8: Serious Adverse events per group**

Safety population	Montelukast N=	Placebo N=
	Death	
	XXX	
	XXX	
	...	
Data are n (%)
